5.6.4 Buprenorphine protocol consent process

Patients who are randomized to expanded taper options will receive initial information about buprenorphine rotation from their intervention clinician (i.e., TCM clinical pharmacist, IPT medical provider, or IPT clinical pharmacist). Those who are interested in learning more will be scheduled for a visit with a buprenorphine prescriber. This visit may be conducted in-person, by video, or by telephone per patient preference and local site visit availability. Face-to-face (in person or video) visits are preferred, but telephone visits are acceptable if allowed by current regulations and policies. This visit will include assessment of buprenorphine appropriateness, discussion of risks and benefits of buprenorphine rotation, and provision of buprenorphine educational materials and resources. The local site coordinator (or other study staff approved to obtain informed consent) will attend this visit if acceptable to the patient or meet with the patient and prescriber as soon as possible (in person, via video or telephone) afterwards to ensure the study protocol is followed (e.g., informed consent process is completed before buprenorphine is prescribed). If the prescriber determines buprenorphine is clinically appropriate and the patient would like to proceed with buprenorphine rotation, the local site coordinator (or other study staff approved to obtain informed consent) will complete the buprenorphine informed consent process.

To ensure patients make a fully informed decision about the buprenorphine protocol, written informed consent for the buprenorphine protocol will occur after the initial visit with the buprenorphine prescriber. Timing of the informed consent process may be immediately after this visit or at a later date if the patient would like additional time to consider.

For buprenorphine protocol appointments conducted by video or telephone, study personnel will mail the patient buprenorphine informational materials and two copies of the informed consent document prior to the appointment. Study personnel will ask patients to sign one copy of the consent form and mail it back, using a study provided postage-paid envelope. Patients will be instructed to keep the second copy. Upon receipt of the signed informed consent form, the local study coordinator/research assistant (or other study staff approved to obtain informed consent) keep it on file. Study staff will

make a copy and provide it to the local research pharmacy. A signed copy will also be mailed back to the patient.

5.6.5 Buprenorphine visit schedule

The initial buprenorphine visit with the buprenorphine prescriber may occur by any mode allowable by current regulations, as described above, but face-to-face (i.e., in-person or video) is preferred. First visit tasks include the following:

- Obtain history of current opioid use; assess buprenorphine risk factors (including risk for pregnancy if applicable)
- Provide standardized buprenorphine educational materials and resources
- Use shared-decision making to determine whether to proceed with buprenorphine rotation
- Document visit on buprenorphine initial visit template

Following buprenorphine initiation, structured follow-up will occur at three time points: 2 days, 1 week, and 3 weeks after initiation. These visits may occur by telephone or face-to-face, as appropriate. Patients will be instructed on whom to contact for problems or concerns occurring between visits. After the three structured visits, follow up will occur according to the assigned TCM or IPT intervention. Most follow-up visits will occur by telephone, although participants will have the option of face-to-face visits. Follow-up visit tasks include the following:

- Assess medication response and adverse effects, including withdrawal symptoms as appropriate
- Administer standard satisfaction questions
- Provide additional education and counseling as needed
- Document visit on buprenorphine follow-up visit template

5.7 Intervention Management of Adherence and Adverse Effects

5.7.1 Clinical monitoring of opioid adherence

The approach to opioid monitoring will augment, rather than replace, primary care management. Prior to the initial visit, intervention teams will review prior drug testing results and opioid fill patterns and determine whether local and national VA monitoring requirements have been met. If a patient is past due for any monitoring tasks, intervention clinicians will work with the primary care team to complete them. In addition, the PDMP will be checked and checklist of opioid non-adherence behaviors will be completed at each medication management visit.

5.7.2 Clinical management of opioid-related risk and opioid adherence problems

Intervention clinicians will facilitate use of opioid risk reduction strategies, including use of naloxone rescue kits, which are recommended by CDC guidelines for patients on moderate-to-high dose opioid therapy.

If opioid adherence problems are identified, they will be evaluated and addressed by intervention clinicians with the goals of improving both pain management and safety. Nonadherence behavior will be discussed at intervention case review meetings and an

individualized monitoring plan will be developed to aid in diagnosing and addressing the underlying cause of the behavior. This plan may include: a) education; b) medication adjustment; c) additional study or primary care visits; d) review of state PDMP database; e) urine drug testing; f) shorter prescription intervals; or g) referral to a mental health or addiction clinician.

5.7.3 Clinical management of opioid use disorder (OUD)

Intervention clinicians will be instructed to evaluate patients with symptoms or signs of OUD or other SUD to establish a diagnosis. OUD diagnostic criteria will be included in study templates for easy reference. The opioid dose reduction strategies proposed in this study are not sufficient treatment for opioid use disorder, so intervention clinicians will facilitate evidence-based addiction treatment for participants who receive an OUD diagnosis during the study. Depending on local site resources and usual care processes, addiction treatment may be integrated with primary care or may be delivered in an addiction specialty clinic. Regardless of the setting and degree of addiction care integration, intervention clinicians will collaborate with addiction treatment providers to maximize coordination of care for study participants. Participants who are diagnosed with OUD will continue to receive non-opioid analgesic and non-pharmacological therapies for their pain in their assigned TCM or IPT pain management arm. OUD will not be cause for withdrawal from the trial.

5.7.4 Clinical management of adverse effects

Medications will be prescribed and monitored by intervention clinicians according to usual standards of care and relevant clinical guideline recommendations. Prior to the start of trial enrollment, intervention clinicians involved in medication management will be provided with additional training on medication indications, contraindications, and interactions. Specific training will be provided to intervention clinicians on care of reproductive-aged women, including women who are pregnant, lactating, or could possibly be pregnant. Study medication management reference documents and educational tools will be available to all intervention clinicians on the study SharePoint site. The study pharmacist coordinator will ensure study medication management guidance is up-to-date and available throughout the study and will serve as a resource for intervention clinicians at all sites.

Study note templates will include prompts to perform medication reviews, query about contraceptives and potential of pregnancy, and consider potential drug interactions. Study educational materials will address common/important benefits and risks of medications. Educational materials for reproductive-age women will address common/important issues related to pain medications and pregnancy.

Study templates will also include prompts to inquire about treatment-related side effects and adverse symptoms. Intervention clinicians will manage these symptoms according to usual standards of clinical care, offering treatment for minor injuries and adjusting or discontinuing therapies as appropriate.

5.8 Intervention Fidelity

Delivery of intervention components will be tracked to ensure that patient participants at each site receive the core elements of each intervention and also to describe heterogeneity in intervention implementation and use of optional elements across sites. Intervention-specific

CPRS note templates will generate centrally retrievable electronic data elements (i.e., health factors), allowing us to measure the number and types of study visits attended by participants and examine aspects of intervention intensity and fidelity.

The research team will monitor fidelity to core intervention elements throughout the active intervention phase of the trial. Data generated from use of note templates and other sources will be used to populate internal study fidelity reports. Fidelity reports will include summary data across and within sites. Reports will be reviewed and discussed at least every 6 months on all-site meetings and DSMB meetings. If site or intervention arm-specific problems are identified, these will be addressed with involved research personnel or intervention clinicians.

5.8.1 IPT motivational interviewing (MI) fidelity

Because behavioral activation sessions are a defining element of the IPT intervention, fidelity to MI principles in these sessions will be assessed using the Motivational Interviewing Treatment Integrity (MITI, v 4.2) coding instrument. The MITI will be used to rate audio-recordings of a sub-sample of audio-recorded behavioral activation telephone sessions. For this pragmatic trial, fidelity monitoring will focus on training in initial sessions; later assessments will allow better understanding of intervention processes. Interventionists will be instructed to record all sessions to avoid selection bias (e.g., only providing “good” sessions to the research team). For the initial several months after the start of study enrollment, we will randomly select 10% of the recorded behavioral activation sessions. Two co-investigators will use the audio-recordings to code sessions for MI fidelity. After IPT clinicians demonstrate MI competency based on MITI ratings, we will continue to monitor MI fidelity in 5% of randomly selected visits. Finally, 1% of sessions coded with the MITI will be double-coded to establish inter-coder reliability.

5.9 Intervention Discontinuation and Transitions of Care

TCM/IPT intervention clinicians will assume primary management of chronic pain care for patients while they are participants in the study. Chronic pain management by the intervention clinicians will last 12 months unless the patient does not want to continue for the full 12 months. Patient participants may elect to discontinue active intervention participation for any reason at any time.

Patients will be encouraged to receive their chronic pain care from the TCM/IPT throughout their participation in the study; however, patients will not be restricted from seeking pain care from their PCP or other providers. Patient participants may continue in the study regardless of adherence to intervention protocols.

Chronic pain care will be transitioned from intervention clinicians back to the PCP when the patient completes participation in their assigned intervention. For most patients, this transition will occur at the scheduled end of their 12-month study participation after the final intervention visit. For patients who stop active participation in the intervention of their own accord, this transition will occur when they indicate their desire to discontinue participation.

Regardless of when and why the transition back to the PCP occurs, intervention clinicians will retain responsibility for chronic pain care (e.g., active medications, referrals) until the PCP accepts responsibility for the patient’s pain care (i.e., the handoff is complete). The processes outlined below will be used to ensure continuity of care:

- Intervention clinicians will place a templated summary clinical care note in the patient's medical record with the patient's PCP added as a cosigner.
- Intervention clinicians will check the state prescription monitoring program and include information about outside prescriptions in the transition note.
- Intervention clinicians will contact PCPs directly to discuss anticipated transition needs or challenges. PCPs will be encouraged to contact intervention clinicians with any concerns.
- Patients will be encouraged to contact their intervention clinicians if they have any questions or concerns about the transition in their pain care.
- If intervention clinicians are prescribing medications at the end of the patient's study participation period, an updated prescription order will be entered in the medical record by the intervention prescriber and flagged for the PCP to sign. If needed to prevent gaps in medication availability, a limited medication supply will be prescribed by the intervention prescriber to cover patient needs until the PCP resumes prescribing.

6. STUDY DATA COLLECTION

6.1 Data Collection Overview

Three types of data will be collected for research purposes: 1) patient-reported measures; 2) administrative data; 3) qualitative data.

6.2 Patient-reported measures

Patient-reported measures, including outcomes and covariates, will be collected by interview at baseline and at 3, 6, 9, and 12 months. The baseline interview will be conducted by the local site study coordinator or research assistant after the patient provides verbal informed consent and before randomization. Follow-up outcome assessments will be conducted as telephone interviews by coordinating center research personnel who are masked to treatment arm assignment. Visual aids will be mailed to participants in advance so they can follow along with the interviews. If participants are unable to complete 6 or 12-month telephone interviews, they will be offered the alternative of completing mailed paper questionnaires. Participant responses will be recorded on machine-readable paper questionnaire forms, which will be subsequently double-scanned into an electronic database. Interviews are completed with the most critical measures first, to prevent missing core outcome data in case of interruption.

6.2.1 Timing and duration of assessment interviews

Full-length assessment interviews will be conducted at baseline, 6 months, and 12 months. The duration of assessment interviews will be approximately 60 minutes at baseline and 45 minutes at 6 and 12 months. A small participant payment (\$50 each) will be provided after each of these interviews. A nominal token of appreciation (e.g., jar opener with study logo) will be sent to participants before the 12-month interview.

Abbreviated assessment interviews addressing core outcome measures will be conducted at 3 and 9 months. The duration of these abbreviated interviews will be approximately 15-20 minutes. A small participant payment (\$25 each) will be provided after each abbreviated interview.

Timing of follow-up assessment interviews will be based on the date of the baseline interview. Follow-up assessments may be completed up to 30 days early when extenuating circumstances (e.g., planned travel or move) suggest that data may be otherwise lost. 3 and 9 month assessments may be completed up to 30 days late. 6 and 12 month assessments may be completed up to 60 days late. Data from assessments completed outside of these time windows will not be included in primary analyses.

If the first intervention visit is delayed >30 days after baseline assessment date, participants will be asked to repeat core baseline measures (administered by masked assessors), prior to the first intervention visit. A small participant payment (\$25 each) will be provided after the abbreviated, repeat baseline interview.

At the end of the 12-month interview, the assessor will ask for permission to re-contact the Veteran, either for a qualitative interview (described below in 6.4.1) or other future interviews; participants will be reminded these future interview(s) are voluntary.

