4.3.8 Enrollment

Eligible patients will have an enrollment appointment with local site study personnel. This enrollment appointment may be conducted in-person, via VA video-telehealth technology, or by telephone, per patient preference and local availability. At this initial appointment, the local site study coordinator or research assistant will provide additional study information, answer any questions, and complete the informed consent process with the patient.

For in-person appointments, patients will be given a folder, pen, pillbox with the study logo, and a \$5 VA canteen service voucher (regardless of whether they join the study). The voucher will allow the patient to purchase water, coffee or a refreshment while they review materials. Local sites will also provide a travel payment to offset transportation costs; these will be paid via pre-paid debit card to patients who attend an in-person enrollment appointment, regardless of whether they enroll in the study. Local sites may opt to give all patients the same flat travel payment (between \$20-50) or use a tiered system based on distance from patients' home.

For appointments conducted by video or telephone, study personnel will mail the patient a packet containing folder, pen, pillbox with the study logo, pre-paid debit card (containing no value, to be used for incentive payments after each completed study interview) and two copies of the informed consent document and HIPAA authorization forms. Study personnel will ask patients to sign one copy of the consent form and HIPAA authorization and mail it back, using a study provided postage-paid envelope. Patients will be instructed to keep the second copy. Upon receipt of the signed informed consent and HIPAA authorization forms from the participant, the local study coordinator/research

assistant will keep them on file, per local policy. She/he will make a copy of the signed consent and HIPAA authorization forms and mail them back to the patient for his/her records.

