Participants are not considered enrolled until the signed written informed consent and HIPPA authorization forms are received. If the signed consent and HIPAA authorization forms are not received within 14 days, study personnel will follow-up with the patient by telephone to determine interest in participation and troubleshoot problems with the forms or mail. Replacement copies will be provided, if needed. If the signed consent/HIPAA forms are received after 45 days, baseline outcome measures must be repeated prior to randomization. If study personnel do not succeed in contacting the patient by 45 days after the enrollment visit, no additional attempts will be made.

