4.3.9 Randomization

After obtaining the written informed consent document (either in person or upon receipt of the original mailed copy) and completing the baseline interview, the local site coordinator/research assistant will initiate randomization using the study application randomization form. The randomization code will not be visible to personnel conducting randomization and can be completed only once per study ID, preventing study personnel from influencing treatment allocation. This process will simultaneously inform the coordinator and participant of the primary study arm assignment. To prevent patients from feeling pressured to taper opioids, the taper option assignment will be revealed only when participants agree to discuss options for opioid dose reduction. Regardless of whether the taper intervention is delivered, participants will be evaluated in their assigned arm.

Patients will be randomized within site and opioid dose (i.e., moderate or high) categories, in permuted blocks of size 4 or 8, to balance the proportions of participants with moderate-dose and high-dose opioid therapy in the intervention arms. Those in the moderate-dose group will be randomly assigned, with equal likelihood, to intervention arms. Those in the high-dose group will be randomly assigned, with equal likelihood, to intervention and tapering strategy combinations.

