6.3.2 Opioid dispensing data

Opioid dose outcomes and medication covariates will be assessed using VA outpatient pharmacy dispensing data. Opioid daily dose at any given time will be calculated as the mean dose over the prior 90 days, so the main opioid dose outcome will therefore be an average dose over the final 90 days of the study intervention period. To provide information about dose after the intervention is complete, our final dose assessment time-point will be three months after the end of the study. Established conversion tables will be used to calculate morphine-equivalent (ME) mg.

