7.7 Analysis of Adverse Events

Information about hospitalizations, ED visits, SUD admissions, and other adverse events will be extracted from VA administrative data. We will compare intervention arms with respect to the 1) proportion of individuals reporting any hospitalization, ED visit, and SUD admission and 2) number of hospitalization, ED visit, or SUD admissions per person at a) each assessment time-point and b) overall using, respectively, Pearson chi-square tests and, given the reasonable large sample in each arm, large sample normal approximation based z-tests. Similar comparisons will be made between other adverse events. We will also break these comparisons out by baseline dosage and assignment to the expanded taper options arm.

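### Follow-up is dated from the baseline interview rather than randomisation, so participants enrolled with mailed consent can have less time on their assigned arm at each nominal visit

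*Combined protocol and SAP*

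**What the plan says.** All references are to the combined protocol and SAP.

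- **Clock.** Section 6.2.1: "Timing of follow-up assessment interviews will be based on the date of the baseline interview". The permitted windows are set around those dates: 30 days early in extenuating circumstances, 30 days late at months 3 and 9, and 60 days late at months 6 and 12. Assessments outside the windows are left out of the primary analyses.
- **Order of events.** Section 6.2 places the baseline interview "after the patient provides verbal informed consent and before randomization". Section 4.3.9 allows randomisation only "After obtaining the written informed consent document (either in person or upon receipt of the original mailed copy) and completing the baseline interview".
- **Enrolment mode.** Section 4.3.8: "This enrollment appointment may be conducted in-person, via VA video-telehealth technology, or by telephone". For video and telephone, the signed form is returned by post.
- **Repeat baseline, first rule.** Section 4.3.8: "If the signed consent/HIPAA forms are received after 45 days, baseline outcome measures must be repeated prior to randomization".
- **Repeat baseline, second rule.** Section 6.2.1: "If the first intervention visit is delayed >30 days after baseline assessment date, participants will be asked to repeat core baseline measures". The repeat is done by masked assessors before that first visit.
- **Length of management.** Section 5.9 gives 12 months. Sections 5.3.2 and 5.4.2 place the final intervention visit after the 12-month assessment.
- **Dose and events.** Section 6.3.2 says "the main opioid dose outcome will therefore be an average dose over the final 90 days of the study intervention period". Section 7.7 compares events "at a) each assessment time-point and b) overall". Neither section gives a date of origin.

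**The concern.** The treatment clock cannot start before randomisation, but the measurement clock starts at the baseline interview. In person, the two can fall on the same day. With mailed consent they can be weeks apart, and the gap always acts in the same direction: less time since assignment at the nominal visit. Because the final intervention visit is tied to the 12-month assessment, a delayed participant reaches the primary time point before the 12 months of management in 5.9 have been delivered.

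The two repeat-baseline rules leave a further gap. Neither says whether a repeat restarts the follow-up clock, or which baseline enters the primary outcome of a 30% reduction in BPI (7.3). The second rule is triggered by the date of the first intervention visit, which follows randomisation. That repeat can therefore be taken after participants know their primary arm (4.3.9), and the time to a first visit could differ between arms. If such a repeat replaced the earlier baseline, a post-randomisation measurement would help to define the primary outcome.

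**Working it through.** **1. The plan's own figure.** Section 7.1 uses 776 participants with 12-month data out of 970, or 388 per arm. Section 7.1.1 assumes 50% response under TCM. With two-sided alpha 0.05,

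power = Φ{[d√n − 1.96√(2p̄(1−p̄))] / √(p₁(1−p₁) + p₂(1−p₂))}, where d = p₂ − p₁ and p̄ is the mean of p₁ and p₂.

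- n = 388, 50% v 60%: (1.970 − 1.379)/0.700 = 0.844, so power is 80.1% (plan: 80%).
- n = 388, 50% v 61%: power is 87.1% (plan: above 85%).

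The stated power reproduces and is not in dispute.

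**2. Time since randomisation at the nominal visit.** Days = nominal day (91, 183, 274, 365) − lag. The documents give no lag distribution, so three values mark the range: 14 days (when staff chase missing forms, 4.3.8), 30 days (the trigger in 6.2.1) and 45 days (the trigger in 4.3.8).

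| Lag | Month 3 | Month 6 | Month 9 | Month 12 |
|---|---|---|---|---|
| 0 | 91 | 183 | 274 | 365 |
| 14 | 77 (15% shorter) | 169 (8%) | 260 (5%) | 351 (4%) |
| 30 | 61 (33%) | 153 (16%) | 244 (11%) | 335 (8%) |
| 45 | 46 (49%) | 138 (25%) | 229 (16%) | 320 (12%) |

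**3. Which row applies.** The first intervention visit follows randomisation, so any lag of 31 to 45 days also triggers the repeat in 6.2.1. If that repeat resets the clock, the largest uncorrected lag is 30 days. If it does not, the 45-day row stands. Nor is 45 days a cap: forms arriving later lead to a repeat baseline and then randomisation, with no stated upper limit. In the other direction, 6.2 requires only that the interview fall between verbal consent and randomisation, so the gap can be shorter than the postal delay.

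**4. The windows.** Adding them to a 45-day lag:

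- Month 3: 46 − 30 = 16 to 46 + 30 = 76 days since randomisation.
- Month 12: 320 − 30 = 290 to 320 + 60 = 380 days.

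The 12-month window spans 30 + 60 = 90 days, twice the lag. An interview exactly 365 days after randomisation would be 45 days late on the baseline clock, inside the 60-day limit. At months 3 and 9 the same 45 days exceeds the 30-day limit, and the interview would be excluded.

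**5. Possible dilution at month 12 (illustration only).** Assume that the 10-point effect builds up linearly over 365 days and that a share f of participants has the full lag: d = 0.10 × (1 − f × lag/365).

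| f | 30-day lag: d, power | 45-day lag: d, power |
|---|---|---|
| 0 | 0.100, 80.1% | 0.100, 80.1% |
| 0.25 | 0.098, 78.4% | 0.097, 77.5% |
| 0.5 | 0.096, 76.6% | 0.094, 74.8% |
| 1 | 0.092, 72.9% | 0.088, 68.9% |

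The documents give neither f nor the shape of accrual. The row f = 1 is an outer bound, since in-person enrolment involves no postal delay. If the effect has levelled off before about month 10, there is no loss.

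**The case against.** The best defence is that anchoring on baseline is a legitimate choice. The primary outcome is change from baseline, and this clock gives everyone the same nominal interval for that change. A randomisation clock moves the variation elsewhere: with a 45-day lag, the change score would span 365 + 45 = 410 days. The primary test is at month 12, where the shortfall is at most 12% in the range shown and is smaller than the permitted visit window. The lag precedes allocation, so it is balanced between arms in expectation. Opioid tapering is individually timed in any case.

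Most of this stands, and it keeps the point minor. It does not remove it. A window is a tolerance around a target, whereas the lag moves the target, in one direction and by enrolment mode. The defence also leaves open which baseline counts after a repeat.

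Three stronger readings are tempting, and the documents do not support them:

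- **That the composite pairs pain and dose from different dates.** Section 1.1.1 defines both from baseline to 12 months, and the final intervention visit is tied to the 12-month assessment. No section starts the intervention period at randomisation. The dose window's origin is unstated, which is all that can be said.
- **That adverse events before randomisation are counted.** Section 7.7 gives no start date. Section 10.5.1.1 monitors enrolled participants, and 4.3.8 does not regard anyone as enrolled until the forms arrive; that concerns safety monitoring rather than the 7.7 extraction. The interval is undefined, not shown to be wrong.
- **That drift in effect with enrolment date arises by construction.** The revision history adds telehealth enrolment in version 6.0 (June 2018) and telephone in version 12.0 (October 2020). The share of participants by mode is not given, so drift is possible but not demonstrated.

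**Conclusion.** The point holds as a minor one that is cheap to improve. Under the text of 6.2.1, 6.2, 4.3.8 and 4.3.9, time since assignment at a nominal visit can be shorter for participants enrolled by video or telephone, and the 12-month assessment can precede the completion of 12 months of management. Over lags of 30 to 45 days the shortfall is 33% to 49% at month 3 and 8% to 12% at month 12. The upper figures assume that the repeat baseline does not reset the clock. The actual size depends on the lag distribution and the remote share, and the documents give neither.

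A reader might infer bias in TCM versus IPT. The consent lag arises before allocation, so it does not by itself produce any; the consequence is mild dilution, mainly at the earliest visit. The stated sample size and power are unaffected as calculated. The firmest gap in the text is the silence on which baseline and which clock apply after a repeat.

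**What to change.** - **6.2.1:** date the 3-, 6-, 9- and 12-month assessments and their windows from randomisation for every participant.
- **6.2.1 and 7.3:** state that a repeat baseline does not reset the clock, and that the last baseline taken before randomisation is the one used for the 30% reduction.
- **6.3.2:** define the main dose window as the 90 days ending 12 months after randomisation.
- **7.7:** count events from randomisation.
- **Participants already followed on the baseline clock:** report the gap from baseline interview to randomisation by arm and enrolment mode, and add a sensitivity analysis of the 12-month result that places assessments by days since randomisation. This also covers the mixture of clocks if the rule changes part-way through.

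The cost is a date rule in the study application and a few sentences of analysis text. The analyses for participants already followed need no new data, and the sample size does not change. The drawback is that remote enrollees finish a few weeks later and their change scores span a slightly longer interval.
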